## 7.1 Determination of Reporting Requirements

The clinical research team is responsible for collecting and recording the research data. As these results are collected, all toxicities and adverse events will be identified and reported to the principal investigator (PI). The principal investigator (PI) will determine final relationship of the event to the investigational product (ascorbate):

- Grade 1 and 2 events do not require attributions assigned.
- Grade 3 and higher adverse events require attribution assigned to ascorbate.

Toxicity will be graded according to NCI's Common Toxicity Criteria (CTCAE v5). The principal investigator will have final responsibility for determining the attribution of toxicity as it is related to the investigational product.

## 7.2 Institutional Review Board reporting requirements

Adverse events that meet criteria of both *serious* and *attributed* (possible, probable, or definite) to the study agent. Thus:

- Serious adverse events *only*
- Attributable to ascorbate (i.e., drug related)
- Report to the IRB *via* HawkIRB within 10 business days of event

## 7.3 FDA reporting requirements [[name], sponsor]

Adverse events meeting the criteria of *serious*, *unexpected*, and *attributed* (possible, probable, or definite) to ascorbate must be reported by the sponsor or the sponsor's appointed designee to the FDA:

- Serious adverse events *only* [21 CFR 312.32]
- Attributable to ascorbate with a causal relationship (possible, probable, or definite)
- Unexpected, as defined by the FDA: "...not listed in the investigator brochure or is not listed at the specificity or severity that has been observed; or, if an investigator or, if an investigator brochure is not required or available, is not consistent with the risk information described in the general investigational plan or elsewhere in the current application, as amended."

To help the sponsor meet these reporting requirements, all serious adverse events that are unexpected and attributed to study drug must be reported to the sponsor within 1 business day. This coincides with SAE reporting requirements for the DSMC.

## 7.4 Routine Adverse Event Reporting Requirements to DSMC

An adverse event (AE) is defined in the *CTEP, NCI Guidelines* [2005] as "any unfavorable and unintended sign (including a clinically significant abnormal laboratory finding), symptom or disease temporally associated with the use of a medical treatment or procedure (attribution of unrelated, unlikely, possible, probably or definite)."

Routine adverse events are captured in OnCore, the clinical trials management system, for review and assessment by the P.I., sponsor, medical monitor, and DSMC.

## 7.5 Serious Adverse Event Reporting to DSMC

For any experience or condition meeting the definition of a serious adverse event (SAE; 21CFR312.32), from the first day of study treatment and typically continue through the 30 day follow-up period after treatment is discontinued.

Investigators must report to the DSMC any SAE, regardless of attribution to study drug. SAEs must be reported *via* an OnCore SAE Report within 1 business day of learning of the event.

An adverse event is considered **serious** if it results in ANY of the following outcomes:

- Death
- A life-threatening adverse event
- An adverse event that results in inpatient hospitalization OR prolongation of existing hospitalization for  $\geq 24$  hours
- A persistent or significant incapacity or substantial disruption of the ability to conduct normal life functions
- A congenital anomaly/birth defect.
- Important Medical Events (IME) that may not result in death, be life threatening, or require hospitalization may be considered serious when, based upon medical judgment, they may jeopardize the patient or subject and may require medical or surgical intervention to prevent one of the outcomes listed in this definition. ([21 CFR 312.32](#); [ICH E2A](#) and [ICH E6](#)).

## 8. PHARMACEUTICAL INFORMATION – ASCORBIC ACID INJECTION, ASCOR L 500®

### 8.1 Availability

IND 137968 allows ascorbate to be obtained through McGuff Pharmaceuticals (Santa Ana, CA). Their product Ascor L 500® is now a commercially available injection available in sterile single-use 50 mL vials containing 25 g of ascorbic acid (500 mg/mL).

### 8.2 Compatibility

Ascorbate is considered a CYP4503A4 inhibitor. Therefore close monitoring of subjects who may be concomitantly receiving CYP3A4 substrates with narrow therapeutic indexes for toxicities is required. A table of CYP3A4 substrates, inhibitors, and inducers is provided in the Appendix. Ascorbate may decrease plasma/blood concentrations of substrates (Appendix B, tables 1, 2, and 3). Ascorbate may increase CYP3A4 induction (Appendix B, Table 4).

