- 4.2.14 Uncontrolled intercurrent illness including, but not limited to, ongoing or active infection, symptomatic congestive heart failure, unstable angina pectoris, cardiac arrhythmia, or psychiatric illness/social situations that would limit compliance with study requirements.
- 4.2.15 Known HIV-positive and hepatitis B & C individuals. High-dose ascorbate acid is a known CYP450 3A4 inducer, which results in lower serum levels of antiretroviral drugs
- 4.2.16 Patients who are on warfarin and cannot have a drug substitution or who decline the drug substitution.

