## 5.4 Study Timeline Schema:

## Phase 1b schema:

## Phase 2 schema:

## 5.5 Post-consent Screening Procedures

If subjects fail the G6PD or test doses of ascorbate, they are considered a screen failure.

- G6PD test (off-site test, so draw immediately). If subject has a prior G6PD test, this can be used as G6PD levels do not fluctuate (i.e., there is no window for this test).
- One test dose of 15g of ascorbate. A physician must review the patient's medication list against the list of medications prohibited on this trial prior to the test dose of ascorbate.

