## PROTOCOL APPENDIX B: CYP3A4 INTERACTION TABLE

### CYP3A4 INTERACTION TABLE

(Ascorbate may decrease the plasma/blood concentrations of substrates)

Drugs with ~~strikeout~~ text are antiretroviral drugs that are not allowed for use on this study.

\* 3A4 substrate & inhibitor; # 3A4 substrate & inducer

abiraterone	acetaminophen	ado-trastuzumab	alfentanil
alfuzosin	aliskiren	alitretinoin	almotriptan
alprazolam	ambrisentan	amiodarone*	amitriptyline
amlodipine	amprenavir	apixaban	aprepitant*
aripiprazole	armodafinil#	artemether	asenapine
astemizole	atazanavir*	atorvastatin	avanafil
axitinib	beclomethasone	bedaquiline	benzphetamine
bexarotene	bisoprolol	boceprevir	bortezomib
bosentan#	bosutinib	brentuximab	bromazepam
bromocriptine	budesonide	buprenorphine	buspirone
busulfan	cabazitaxel	cabozantinib	caffeine
canagliflozin	carbamazepine#	cevimeline	chlor diazepoxide
chloroquine	chlorpheniramine	ciclesonide	cilostazol
cinacalcet	cisapride	citalopram	clarithromycin*
clindamycin	clobazam	clomipramine	clonazepam
clopidogrel	clorazepate	clozapine	cobicistat*
cocaine	codeine	colchicine	conivaptan*
crizotinib	cyclobenzaprine	cyclophosphamide	cyclosporine*
dantrolene	dapsone	darifenacin	<del>darunavir</del>
dasatinib	delavirdine*	desogestrel	dantrolene
dexamethasone#	dexlansoprazole	dextromethorphan	diazepam
diclofenac	dienogest	dihydroergotamine	diltiazem*
disopyramide	docetaxel	dofetilide	dolasetron
domperidone	donepezil	doxorubicin	dronedarone
droperidol	dutasteride	efavirenz*#	eletriptan
elvitegravir	enzalutamide	eplerenone	ergoloids
ergonovine	ergotamine	erlotinib	erythromycin*
escitalopram	esomeprazole	estazolam	estradiol
estradiol valerate	estrogens	eszopiclone	ethinyl estradiol
ethosuximide	etonogestrel	etoposide	etravirine
everolimus	exemestane	felbamate	felodipine
fentanyl	fesoterodine	fexofenadine	finasteride
fingolimod	flunisolide	flurazepam	flutamide
fluticasone	<del>fosamprenavir</del> *	fosaprepitant	fulvestrant
galantamine	gefitinib	gransetron	guanfacine
haloperidol*	hydrocodone	hydrocortisone	ifosfamide
iloperidone	imatinib*	imipramine	indacaterol
<del>indinavir</del> *	irinotecan	isosorbide dinitrate	isosorbide mononitrate

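### Section 8.2 calls ascorbate a CYP3A4 inhibitor and orders monitoring for toxicities on that basis, while the rest of 8.2, exclusion 4.2.15 and Appendix B point to induction or lower substrate levels

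*Combined protocol and SAP*

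**What the plan says.** Section 8.2 (Compatibility) opens with "Ascorbate is considered a CYP4503A4 inhibitor", citing reference 40. The next sentence draws a required action from it: "Therefore close monitoring of subjects who may be concomitantly receiving CYP3A4 substrates with narrow therapeutic indexes for toxicities is required". The same short section then ends with two statements that point the other way: "Ascorbate may decrease plasma/blood concentrations of substrates" and "Ascorbate may increase CYP3A4 induction". Each of these refers the reader to tables in Appendix B.

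Exclusion 4.2.15, which keeps out subjects known to have HIV or hepatitis B or C, gives as its reason: "High-dose ascorbate acid is a known CYP450 3A4 inducer, which results in lower serum levels of antiretroviral drugs". The heading of the Appendix B table, repeated on its continuation page, reads "Ascorbate may decrease the plasma/blood concentrations of substrates".

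Three provisions deal with single drugs or drug classes. Exclusion 4.2.15, with the strikeouts in Appendix B, deals with antiretrovirals. Exclusion 4.2.16 deals with subjects on warfarin who cannot have, or decline, a substitute. Section 5.8.1 cautions that ondansetron may work less well with ascorbate.

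**The concern.** Inhibition and induction call for different clinical vigilance. If ascorbate inhibits CYP3A4, substrate levels rise and toxicity is the hazard. If it induces CYP3A4, levels fall and the hazard is loss of effect. The protocol acts on induction in one place, where it excludes HIV-positive subjects because antiretroviral levels would fall. It acts on inhibition in another, where it orders monitoring for toxicities.

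The inconsistency therefore sits in the premise of a required safety action, and is more than an untidy background sentence. If the premise has the wrong sign, staff who follow the order as written are told to look for the less relevant problem. For a drug with a narrow therapeutic index, a fall in effect could do harm before anyone looks for it. Adverse-event reporting would record the result but would not prevent it.

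**Working it through.** No arithmetic in the plan bears on this point, and there is no stated figure to reproduce. The check is a comparison of every statement on the direction of the interaction.

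1. **Statements for inhibition.** There is one: the first sentence of 8.2. The monitoring order in the second sentence is derived from it and is not separate evidence.

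2. **Statements for induction or lower levels.** There are four: the sentence in 8.2 on decreased substrate concentrations, the sentence in 8.2 on increased induction, exclusion 4.2.15, and the Appendix B heading (counted once although it appears on two pages). The tally is 1 against 4. The four are not fully independent, because the closing sentences of 8.2 cite Appendix B. Exclusion 4.2.15 makes its statement without citing Appendix B.

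3. **Statement compatible with induction.** Section 5.8.1 expects ondansetron, which Appendix B lists, to be less effective. It names no mechanism, so it is left out of the count.

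4. **Can the true direction be read from the documents?** No. Section 8.2 rests on reference 40, whose title says only that it studied the effect of high-dose vitamin C on CYP3A4 activity. The weight of the text favours induction; that is evidence of what the authors meant, not of the pharmacology.

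5. **What follows if induction is right?** The order in 8.2 names toxicities and does not mention loss of effect. The medication review before the test dose (section 5.5 and calendar footnote i) compares the subject's "medication list against the list of medications prohibited on this trial", so it does not address drugs that are allowed. Section 5.8 leaves supportive-care prescribing to the investigator and asks that it be recorded. The single-drug provisions cover antiretrovirals, warfarin and ondansetron. In the text available, no general order covers loss of effect of other substrates.

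6. **Could such a subject be enrolled?** Yes, under the criteria as written. Exclusion 4.2.12 admits subjects with treated brain metastases and lets them take a stable dose of an anticonvulsant. Carbamazepine is on the Appendix B list and is not barred by name in 4.2.11, 4.2.15 or 4.2.16. The same holds for tacrolimus and cyclosporine. The documents do not label any of the three as narrow-index; that is an assumption from ordinary clinical knowledge.

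7. **What follows if inhibition is right?** The order in 8.2 then matches its premise. The reason given in 4.2.15, the last two sentences of 8.2 and the Appendix B heading would be wrong. An edit is needed either way.

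**The case against.** The strongest reply is that this is a one-word slip which the protocol corrects within the same paragraph. A clinician who looks up a drug in Appendix B reads the opposite direction directly above the list. The order asks for monitoring for toxicities but does not forbid attention to anything else. Ordinary safeguards also run alongside it: concomitant medication is recorded until 30 days after the last ascorbate dose, the calendar reviews adverse events and medication in weeks 2 to 5 and off treatment, and a history and physical falls in weeks 1, 3 and 5. The phase 2 target is 25 patients at the recommended dose, with about five weeks of infusions, so exposure is short and the group small.

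Most of this stands and limits how serious the point is. It does not remove the point, because the word in question is the stated ground for a required action, and none of these safeguards tells anyone to look for a falling drug effect.

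A reader might infer three stronger things that the documents do not support.

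- *That nothing anywhere in the plan covers loss of effect.* Section 8.2 cites Appendix B tables 1 to 4, but only one unnumbered table is visible, and no list headed as prohibited medications can be seen. The negative can be claimed only for the text available.
- *That the length of the Appendix B list measures the exposure.* It does not. Only narrow-index drugs matter here, the documents do not identify them, and the list also contains items such as caffeine and acetaminophen.
- *That loss-of-effect monitoring is owed whichever direction is true.* It follows only from induction. Under inhibition, the toxicity order is the matching one.

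**Conclusion.** The contradiction is certain: it can be read directly in 8.2, 4.2.15 and Appendix B. That *inhibitor* is a slip for *inducer* is probable, given one statement against four, but the documents do not prove it.

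The consequence is conditional. It requires that induction is the true direction and that a subject takes a narrow-index substrate not barred by name. It also requires that the clinician follows the order without acting on the rest of 8.2 or on Appendix B. The documents give neither the number of such subjects nor the size of any CYP3A4 effect, so no risk of harm is estimated.

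This is a minor correction to safety text, worth making because the doubtful word drives a required action and the repair is nearly free. It has no bearing on the pathologic response endpoint, the power or the sample size.

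**What to change.** Check what reference 40 shows and make the direction the same in 8.2, 4.2.15 and Appendix B.

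- **If it shows induction:** change *inhibitor* to *inducer* in the first sentence of 8.2, and reword the order. Suggested text: *Subjects receiving CYP3A4 substrates with narrow therapeutic indexes must be monitored closely for loss of effect as well as for toxicity, with drug levels checked where this is standard of care.*
- **If it shows inhibition:** keep the toxicity order as it is, and correct the reason given in 4.2.15, the last two sentences of 8.2 and the Appendix B heading.

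The cost is a wording amendment and, in the first case, slightly broader clinical attention. No study visit or procedure is added: the calendar schedules no co-medication levels, and the suggested text leaves them to usual care.

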### 8.3 Storage and Stability

Unopened vials of are stable until the expiration date indicated on the package when stored between 2° – 8°C (36°–46°F). Protect from light and store in the carton until time of use.

## 8.4 Toxities

### 9. DIARRHEA, NAUSEA AND/OR VOMITING, KIDNEY STONES, DRY MOUTH/THIRST, HEADACHE, ABDOMINAL PAIN, FATIGUE, FACIAL FLUSHING, SWEATING, WEAKNESS, INJECTION SITE IRRITATION, AND FAINT/DIZZY (AFTER RAPID INFUSION), AND HYPERTENSION THAT MAY REQUIRE MEDICATION HAVE BEEN REPORTED. CORRELATIVE AND SPECIAL STUDIES

#### 9.1 ROS Research blood

Research blood for future use will be drawn at:

- Baseline prior to test dose of ascorbate
- Prior to XRT dose 1
- Week 3 of radiation therapy prior to XRT dose
- After last fraction of radiation therapy ( $\leq 60$  minutes of completing that fraction)
- End of study visit which will be  $\sim 1$  month of completing ascorbate therapy

The specimen should be placed on ice immediately after the draw and carried to [name] lab.

Time point	Ascorbate level (4 cc green top)	ROS (6cc pink)	Immuno (6cc pink)
Test Dose	pre	pre	pre
W1D1	30 min post Ascorbate	pre XRT dose	NA
W3D1	30 min post Ascorbate	pre XRT dose	NA
W5	30 min post last Ascorbate dose	$\leq 60$ min post last fraction of XRT	30 min post last Ascorbate dose (or can be drawn with ROS after last fraction of XRT)
30 Day post last Ascorbate	NA	yes	yes

#### 9.2 Labile Iron Measurements using MRI Imaging (optional)

Pharmacological ascorbate's mechanism of action is hypothesized to involve changes in labile iron pools within the tumor. The presence of labile iron and/or iron containing metalloproteins is necessary to oxidize ascorbate and eventually lead to the generation of hydrogen peroxide, thereby increasing tumor cell oxidative stress. *In vitro* laboratory studies demonstrate treating GBM and non-small cell lung cancer (NSCLC) cells with high doses of ascorbate increases labile iron pools. Additionally, chelating (e.g., removing) iron from tissue culture media reduces pharmacological ascorbate toxicity to tumor cells.

MRI imaging will be done only for extremity sarcoma subjects prior to ascorbate treatment as a pre-scan control (at diagnosis) and will be done at 60 minutes +/- 30 minutes) and 4 hours post ascorbate treatment (in radiation oncology suite during week 3) as it has been seen that ascorbate levels tend to peak between 1 and 2 hours after injection. Imaging studies will be conducted on

a GE 1.5T/3T MRI scanner using appropriate anatomical coils. Images will be acquired using a T2\* fast gradient-echo, multi-echo pulse sequence with short echo time (~6 ms) and repetition time ~25 ms which has shown to be beneficial in previous studies involving iron overload measurements in the liver and heart. Image analysis will initially be done using a region of interest approach in which the tumor region will be contoured and then analyzed using a mono-exponential decay of the T2\* relaxation time. This image analysis has been shown by *Positano, et. al* to be clinically acceptable and more clinically relevant. Serum iron, transferrin saturation, total iron binding capacity and ferritin levels will be obtained to evaluate if they correlate with responses and T2\* imaging findings.

This series will be done at three time points – baseline (as part of simulation in radiation oncology suite or as part of diagnostic MRI if it is being done), week 3 and end of study (as part of diagnosis). The imaging in week 3, done in the radiation oncology suite, is centered around that day's ascorbate infusion. Contrast is not allowed for these sequences and will not be ordered. The following MRI should be ordered to be completed on the same day:

- 9.2.1 **Contrast.** No contrast is to be used (oral or IV)
- 9.2.2 **Scheduling.** The infusional T2\* is scheduled in week 3. The other time points are at RT simulation and end of treatment study (diagnostic)
- 9.2.3 **Pre-infusion (week 3).** A pre-infusion T2\* MR series will be obtained. This will contain both the T2\* and also axial imaging for reference.
- 9.2.4 **Post-infusion (week 3).** 30 to 90 minutes within the end-of-infusion, a second T2\* / axial series will be obtained. This should be obtained prior to the day's radiation therapy.
- 9.2.5 **4h post-infusion (week 3).** The last T2\* / axial series will be done approximately 4h after the end-of-infusion ( $\pm$  60 minutes).

### 9.3 Diffusion Weighted Imaging (optional)

Addition of functional diffusion-weighted MRI (DW-MRI) to standard anatomic and postcontrast MRI greatly facilitates interpretation of response to therapy. After radiation therapy, new enhancement alone can be seen which may be a result of vascular disruption rather than histologic response. Hence should be interpreted carefully. Although currently not a standard clinical trial endpoint, DW-MRI appears to be a promising as a quick, noninvasive tool showing excellent reproducibility for apparent diffusion coefficient measurements, which reflect tumor cellularity and microarchitecture in STS. However, the relationship of these MRI parameter changes with clinical outcomes has not yet been validated. Hence we intend to evaluate this MRI sequence which is currently acquired routinely for imaging brain tumors and stroke. This sequence will be added to the planning MRI acquired in radiation oncology prior to starting radiation therapy treatment and will be compared to the DWI sequence acquired pre-operatively.

### 9.4 Ascorbate levels

Serum ascorbate levels will be drawn at screening, 30 mins post at week 1 day 1, as well as 30 mins post week 3 Day 1 and 30 min post last infusion in week 5. This is being done to ensure a target serum level of 20 mM is reached during treatment.

### 9.5 Tumor tissue

A part of the resected tumor (1 x 1 inch) specimen together with the surrounding normal tissue will be testing for immune markers such as CD4, CD8, T regulatory cells. MDSCs and

macrophages. Flash frozen tissue will be subjected to T2 \* imaging testing to determine labile iron concentrations in comparison to the surrounding normal tissue. Molecular testing including next generation testing may be performed on the paraffin embedded tissue specimens. Optional pre-treatment tumor biopsies will be taken from approximately 5 subjects total and immune markers will be compared between pre and post treatment tissue in the immunology lab.

## 10. STUDY CALENDAR

### 10.1 Study Procedures

	Screen b	Treatment a					Off treatment and end of study c	Follow Up d
		Week 1	Week 2	Week 3	Week 4	Week 5 (+1wk j )		
H & P	X	X		X		X		
Tumor biopsy (optional)	X b							
Performance status	X						X	X
Clinical MRI/ Staging CT	X						X	X e
Pregnancy test k (urine)	X							
G6PD	X							
EKG	X							
CBC w/diff	X			X		X		
PT/INR, PTT & uric acid	X							
Height	X							
Weight, BSA	X						X	
Vitals (BP, pulse) m	X	X	x	X	x	X	X	
Comprehensive metabolic panel (CMP)	X	X		X		X	X	
Ascorbate infusion	X i	XXX	XXX	XXX	XXX	XXX		
Blood for ascorbate levels f	X	X		X		X		
ROS Research blood g	X	X		X		X	X	
Immunology research lab g	X					X	X	
Iron Panel including ferritin h	X						X	
T2* /QSM and DWI MR imaging sequences (optional)	X			X			X	
Adverse Events & Con Meds			X	X	X	X	X	

**a** study day 1 is defined as radiation therapy day 1 (i.e., fraction 1).

**b** screening labs, history, and physical must be obtained  $\leq$  28d from d1. G6PD may be obtained at any time prior to test dose. MRI/CT obtained  $\leq$  28d from d1 (RT sim is acceptable). Pregnancy test per institutional guidelines. Optional tumor biopsy can be done anytime before week 1 dosing.

**c** includes both off-treatment evaluation and study completion. Study completion requires a final study dictated visit 4 to 6 weeks after the last dose of ascorbate. Follow at least monthly until resolution of all ascorbate related adverse events.

**d** approx every 3 months (every 12 weeks [+/- 4 weeks]) for overall survival through passive chart review, phone call or scheduled follow-up visit for 2 years

**e** Imaging as per standard of care for site specific sarcomas

**f** 4cc green-top Na-Heparin tube. Draw pre-infusion at 15g dose, then 30 min post-infusion: week 1 day 1 , week 3 and last infusion of week 5

**g** 6cc pink-top EDTA tube. Draw pre infusion The specimen should be placed on ice immediately after draw and carried to the lab

**h** At time of screening and end of study

**i** Test dose of 15 g intravenously once G6PD levels confirmed to be adequate. A physician must review the patient's medication list against the list of medications prohibited on this trial prior to the test dose of ascorbate.

**j** In case of radiation treatment delays due to holidays

**k**  $\pm 7$  days prior to day 1

- m** Blood pressure should be obtained before and after ( $\leq 15$  min EOI) ascorbate infusion

